1.0 Background

Breast cancer treatment-related lymphedema (BCRL) is a chronic, debilitating disease caused by lymphatic flow obstruction and lymphedema of the upper limb and torso secondary to necessary cancer therapies, namely lymph node removal. BCRL has been reported to occur in 20-30% of breast cancer survivors following these therapies, which is in addition to similar incidence of secondary lymphedema in the upper limb occurring in persons with other therapies necessitating axillary lymph node removal and/or radiation. However, owing to a lack of methodology for sensitively identifying lymphatic system compromise, there are important gaps in our knowledge regarding which patients are at highest risk and how and when therapies should be applied to minimize impairment. Here, novel and noninvasive magnetic resonance imaging approaches for measuring lymphatic dysfunction are applied to improve procedures for preventing, predicting, and treating secondary lymphedema.

The long-term goal of this work is to develop and apply novel tools to visualize lymphatic dysfunction, and also to incorporate these tools to provide new observables that can be used as much needed trial endpoints to optimize therapies and improve patient outcomes. This research initiative which started at VUMC over four years ago has led to the development of new, noninvasive imaging methods for evaluating LN function and morphology here at VUMC, along with approaches for visualizing lymphatic vessels and tissue impairment without exogenous contrast agents. These methods have been applied by us in healthy adults across the lifespan to evaluate normative parameter ranges, in surveillance imaging of BCRL patients at multiple disease stages, and in BCRL patients before and after manual lymphatic drainage (MLD) therapy¹⁻⁴. This work has led to the development of multiple new biomarkers that are more sensitive than traditional external measures of lymphatic dysfunction.

We will build on the development efforts from our previous and ongoing lymphedema research (IRB #131172) to apply methods to evaluate lymphatic dysfunction in multiple stages of secondary lymphedema management, including (i) prevention, (ii) sub-clinical risk identification, and (iii) therapy.

Below summarizes this study's overall significance:

1. We will utilize multi-parametric anatomical and molecular imaging of LNs, which incorporate measures of anatomy and chemical environment, to evaluate abilities to discriminate metastatic from benign LNs noninvasively *in vivo*. These approaches have already been applied in other applications of malignancy⁵⁻⁷, and we have developed innovative high spatial resolution variants to enable sub-millimeter LN characterization *in vivo*¹. If successful, findings would have relevance for noninvasively mapping the topography of LN malignancy, which could initiate future investigations to ultimately inform surgery decisions and reduce unnecessary LN removal.

2. We will extend our current trial to evaluate sub-clinical internal and external risk factors of secondary lymphedema progression in the arm and upper torso following cancer therapies post-LN removal and test more refined hypotheses regarding how impaired lymphatic pumping, superficial axillary water accumulation, and interstitial adipose accumulation portend secondary lymphedema onset and progression. This work will be significant for understanding prognostic potential of the new internal markers relative to existing risk factors, and it will reinforce using these measures to triage patients for disease-modifying therapies or as endpoints in therapeutic trials.

3. Emerging therapies that utilize CDT with refined approaches in the individual components (i.e. incorporating graded negative pressure) are being utilized in specialized lymphedema outpatient clinics including Vanderbilt Lymphedema Clinic, but formal efficacy trials have not been performed. We will perform a multiple-measures cross-over trial to evaluate the impact of CDT with vs. without graded negative pressure on reducing lymph stasis and internal markers of fibrosis in chronic BCRL states, along with a subgroup of 1 time treatment before and after MRI and nonMRI measures for immediate treatment impact investigation. Improved lymphatic flow has demonstrated the ability to induce lymphangiogenesis in pre-clinical studies⁸, and it will be crucial to demonstrate internal improvements in vivo, relative to basic symptomatology changes which can be subjective and difficult to quantify, to underscore the need for expanding healthcare coverage of these disease-modifying therapies.

4. The imaging methods developed evaluate functional and anatomical lymphatic system properties and will be applied in hypothesis-driven studies of BCRL in this work. Owing to the known etiology of overt secondary lymphedema such as BCRL, this condition represents an ideal system to evaluate relationships between tissue physiology, such as adiposity and interstitial protein accumulation, and lymphatic insufficiency. However, the findings should have relevance for improving our understanding of the physiological changes that occur in lymphatic vessels and dependent tissues in other cases of lymphedema or disorders where lymphatic dysfunction is suspected⁹.

2.0 Rationale and Specific Aims

The goal of this work is to apply novel, noninvasive magnetic resonance imaging (MRI) methods for visualizing lymphatic circulation dysfunction to test fundamental hypotheses about secondary lymphedema risk factors and therapies. Breast cancer treatment-related lymphedema (BCRL) arises secondary to surgical axillary lymph node (LN) dissection and irritation, and is a chronic and lifelong condition affecting a high 21.4% of patients receiving common breast cancer therapies. Persons at risk for secondary lymphedema following axillary lymph node removal also include undergoing treatment for other cancers, such as melanoma involving the upper body, necessitating the need for axially

lymph node removal. Reducing condition onset and improving management represent major unmet clinical needs, and emerging efforts focus on improving quality of life through more informed LN dissection and biopsy decisions, optimizing post-surgical complex decongestive therapy (CDT), and exploring novel pharmacological and surgical procedures. However, fundamental gaps in our knowledge persist regarding optimized implementation of these therapies and details of the physiological changes they elicit. The major underlying limitation is that there is a shortage of imaging methods available that can be used to evaluate lymphatic function directly, and there is currently no consensus regarding effective outcome measures for therapeutic efficacy evaluation. Rather, LN removal is frequently based on sentinel LN biopsy and additional subjectivity of the surgeon. Therapy evaluation is frequently based on coarse measurements such as changes in limb volume or patient-reported symptoms, which provide little information on underlying mechanistic changes that could be used to further refine these therapies. As part of our ongoing INFORM clinical trial of lymphedema progression and therapy, we have demonstrated potential for new, noninvasive MRI approaches to identify lymphedema risk in sub-clinical disease stages, as well as to visualize internal changes in lymphatic functioning as a result of emerging therapies. Here, we propose to extend these studies to improve abilities for lymphedema theranostics.

Aim 1: Prevention. We will apply new anatomical and functional LN imaging approaches to identify LN profiles specific to biopsy-confirmed metastatic LNs; findings could be used to better inform LN removal and reduce the incidence of benign LN dissection. We will incorporate healthy female controls to serve as a comparison to the patient population.

Aim 2: Progression. We will improve our understanding of secondary lymphedema risk progression following cancer therapy by testing the hypothesis that superficial tissue profiles and subcutaneous adipose accumulation are more prevalent in patients experiencing lymphedema progression, and thereby could be used to triage patients for aggressive therapies prior to overt symptoms and irreversible damage.

Aim 3: Therapy. We will perform a repeated-measures cross-over trial to test the hypothesis that mobilization of protein enriched hardened tissue using graded negative pressure therapy in conjunction with complete decongestive therapy (CDT) is more effective to standard CDT alone for secondary lymphedema management. Both of these conservative physical therapy treatments are commonly employed for treatment of secondary lymphedema and the Vanderbilt Lymphedema Clinic utilizes the graded negative pressure therapy as a component of treatment. Additionally we will perform a subgroup of 1-time only hour treatment with before and after MRI and nonMRI measurements for additional immediate treatment impact in CDT, CDT with graded negative pressure, or exercise and self management treatment strategies alone as commonly performed in outpatient physical therapy clinics and at home for the management of BCRL.

The overarching goal is to develop objective markers of lymphatic dysfunction that can be used in emerging therapeutic trials of cancer and lymphedema therapies to be used to reduce both the incidence and severity of symptoms associated with this prevalent and chronic condition.

Aim (1). To compare *in vivo* anatomical and novel molecular imaging contrasts between LNs with versus without biopsy-confirmed metastasis.

Hypothesis (1). Biochemical LN profiles quantified from noninvasive chemical exchange saturation transfer (CEST) MRI provide discriminatory potential for distinguishing metastatic versus benign LNs pre-operatively. These biochemical profiles are more discriminatory than anatomical measures of LN morphology.

Aim (2). To identify sub-clinical biomarkers of lymphatic insufficiency using quantitative evaluation of lymphatic vessel anatomy, axillary edema, and interstitial adiposity.

Hypothesis (2). Sub-acute internal imaging markers reflective of tissue microenvironment and interstitial adipose accumulation provide superior discriminatory abilities for portending BCRL progression compared with established risk factors such as BMI, age, and quantity of LNs removed.

Aim (3). To evaluate the impact of CDT with and without graded negative pressure therapy on internal measures of lymphatic dysfunction and edema in patients with chronic BCRL.

Hypothesis (3). Mobilization of protein-enriched hardened tissue using graded negative pressure therapy in conjunction with CDT will reduce (i) superficial markers of interstitial protein accumulation and (ii) lymph stasis, and improve (iii) patient-valued functional outcomes compared to standard CDT and/or exercise and self management treatment strategies.

3.0 Inclusion/Exclusion Criteria

The following subjects will be excluded from all aims of this study:

1. Subjects who have any type of non-MRI compatible bioimplant activated by mechanical, electronic, or magnetic means (e.g., cochlear implants, pacemakers, neurostimulators, biostimulators, electronic infusion pumps, etc.), because such devices may be displaced or malfunction.
2. Subjects who have any type of ferromagnetic bioimplant that could potentially be displaced.
3. Subjects who have cerebral aneurysm clips.

4. Subjects who may have shrapnel imbedded in their bodies (such as from war wounds), metal workers and machinists (potential for metallic fragments in or near the eyes).
5. Minors (younger than 18 years)
6. Pregnant women
7. Subjects who have open wounds on either wrist and / or right ankle because of contraindications with placement of electrodes to obtain the L-DEX U400 readings.

Also excluded are subjects incapable of giving informed written consent:

1. Subjects who are non-English speaking, Children/minors* (Form #1117), Pregnant women/fetal tissue/placenta* (Form #1116), Cognitively impaired* (Form #1118), Prisoners* (Form #1115)
2. Subjects who cannot adhere to the experimental protocols for any reason, or have an inability to communicate with the researcher.
3. Subjects who have limited mental ability to give informed consent, mentally retarded, altered mental status, mental disability, confusion, or psychiatric disorders.
4. Prisoners

To minimize discomfort, we will also exclude subjects who exhibit noticeable anxiety and/or claustrophobia or who exhibit severe vertigo when they are moved into the magnet.

Inclusion criteria for Aim 1:

1. Females (over the age of 18 years) planning to have unilateral or bilateral axillary lymph node removal surgery as a component of their cancer regime
2. or Females (over the age of 18 years) without history of cancer or lymphedema to serve as study controls

Exclusion criteria for Aims 1:

1. Any contraindication to MRI.
2. Any axillary lymph node removal procedure already performed before study visit.
3. Persons who are deemed clinically unsuitable for an MRI by their treating physician
4. Severe claustrophobia
5. Minors (younger than 18 years)
6. To minimize discomfort, we will also exclude subjects who exhibit noticeable anxiety and/or claustrophobia or who exhibit severe vertigo when they are moved into the magnet. All participants will be screened with the safety screening form currently used for research studies on all research MRI scanner
7. Open wounds on right ankle or bilateral wrists for purposes of obtaining external L-Dex extracellular fluid reading.

8. Subjects incapable of giving informed written consent:
 - a. Subjects who are non-English speaking
 - b. Subjects who cannot adhere to the experimental protocols for any reason, or have an inability to communicate with the researcher.
 - c. Subjects who have limited mental ability to give informed consent, mentally retarded, altered mental status, mental disability, confusion, or psychiatric disorders.
9. Prisoners

Inclusion criteria for Aims 2:

1. Females (over the age of 18 years) who have already had unilateral axillary lymph node removal surgery as a component of their cancer regime in the “at risk” side being monitored for lymphedema development.

Exclusion criteria for Aims 2:

1. Any contraindication to MRI.
2. Persons with signs or symptoms of lymphedema before their first MRI study visit for their “at risk side” being monitored for lymphedema development.
3. Persons who are deemed clinically unsuitable for an MRI by their treating physician
4. Severe claustrophobia
5. Minors (younger than 18 years)
6. To minimize discomfort, we will also exclude subjects who exhibit noticeable anxiety and/or claustrophobia or who exhibit severe vertigo when they are moved into the magnet. All participants will be screened with the safety screening form currently used for research studies on all research MRI scanners.
7. Open wounds on right ankle or bilateral wrists for purposes of obtaining external L-Dex extracellular fluid reading.
8. Also excluded are subjects incapable of giving informed written consent:
 - a. Subjects who are non-English speaking
 - b. Subjects who cannot adhere to the experimental protocols for any reason, or have an inability to communicate with the researcher.
 - c. Subjects who have limited mental ability to give informed consent, mentally retarded, altered mental status, mental disability, confusion, or psychiatric disorders.

9. Prisoners

Inclusion criteria for Aim 3:

1. Females (over the age of 18 years) diagnosed with unilateral secondary lymphedema in the upper quadrant and/or extremity following cancer related surgery involving removal of any axillary lymph nodes and/or radiation therapy.

Exclusion criteria for Aims 3:

1. Any contraindication to MRI.
2. Persons who have undergone bilateral axillary lymph node removal and thus are at risk for bilateral secondary lymphedema
3. Persons who are deemed clinically unsuitable for an MRI or lymphedema therapy by their treating physician
4. Severe claustrophobia
5. Minors (younger than 18 years)
6. To minimize discomfort, we will also exclude subjects who exhibit noticeable anxiety and/or claustrophobia or who exhibit severe vertigo when they are moved into the magnet. All participants will be screened with the safety screening form currently used for research studies on all research MRI scanners and the manual lymphatic drainage screening form administered by a licensed lymphedema physical therapist.
7. Open wounds on right ankle or bilateral wrists for purposes of obtaining external L-Dex extracellular fluid reading.
8. Also excluded are subjects incapable of giving informed written consent:
9. Subjects who are non-English speaking
 - a. Subjects who cannot adhere to the experimental protocols for any reason, or have an inability to communicate with the researcher.
 - b. Subjects who have limited mental ability to give informed consent, mentally retarded, altered mental status, mental disability, confusion, or psychiatric disorders.
10. Prisoners

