A custom RWB report will be utilized to identify potential participants. The report will filter on study inclusion/exclusion criteria computable in the EHR and EMR. Additionally, the report will include OK to Contact status, MHAV account status, and ability to receive MHAV messages. The report may also display additional information that will facilitate screening. We will utilize these systems for MHAV mass messaging and Individual Direct to Patient Messaging for out-reach communication.

5.0 **Study procedures**

1. Informed consent will be obtained via e-consent initially and then during initial visit reviewed in a private setting (e.g., an otherwise empty conference room or waiting area) by one of the study Investigators. This initial e-consent will occur as far in advance of the exam as possible, preferably before the day of the study and a KSP will review any questions with patient remotely as needed prior to onset of study. The study participant will be given a copy of the signed consent form at first visit. The subject will be screened for the study inclusion and exclusion criteria including MRI contraindications or MLD contraindications or precautions to determine eligibility of the study.
2. All subjects will complete an MRI screening form in advance of their scheduled visits for any MRI. The MRI screening form will be cleared by the KSPs and MRI technicians prior to scheduling their 1st MRI visit. This MRI screening form will be completed for each MRI scan a subject may have during the course of the study.
3. The informed consent and the MRI screening form will be sent electronically via email to the participant, to be completed before their study visit.
4. Persons will undergo external measurements obtaining weight, height, arm volumetric measurements (Perometer), skin thickness (SkinFibroMeter), and extracellular fluid levels in the arms (InBODY 770, L-Dex and MoistureMeterD/LymphScanner) and upper body (InBODY 770, MoistureMeterD/LymphScanner) and then undergo a non-invasive MRI to evaluate lymph fluid properties in the upper extremities. No MR methods used require the administration of any exogenous contrast agents, and therefore will be completely non-invasive. The visit for non-MRI and MRI measures lasts

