approximately 90minutes. Patients undergoing 2-year monitoring will also undergo these non-MRI measurements at baseline, and every 5-7 months (targeting at 6months) up to 5 total visits within 2 years; and for this same group an MRI will be done at Visit 1 and then as needed based on symptoms, clinical therapies provided increasing risk of lymphedema such as radiation, and non-MRI measures at subsequent follow-up visits within the 2 year time period. For these follow-up visits non-involving MRI, the visits last approximately 30 minutes.

Perometer

L-Dex

LymphaTouch

MoistureMeter D/LymphaScanner

InBODY 770 (Body Composition)

SkinFibroMeter

5. For subjects enrolled in Aim 3 of this study, they will receive the above mentioned non-MRI and MRI measures (#2) at Visits 1, 11, 12 and 22. In addition the MLD screening form will be completed on Visit 1 in preparation for this component of their CDT during subsequent treatment visits, as well as completion of the Functional Outcome Measures (PSFS and UEFI) patient self-reports will be done on Visits 1, 11, 12 and 22 to establish baseline functional level and monitor during treatments. Then they will receive their assigned therapy intervention (CDT alone or CDT with graded negative pressure) at Visits 2-10 and 13-21. For Group 1, the first course of treatment will be CDT alone, then the second course of treatment will be CDT with graded negative pressure. For Group 2, the first course of treatment will be CDT alone, then the second course of treatment will be CDT with graded negative pressure. During all courses of treatment, it will consist of 9 visits within 6-8 weeks at 75minutes duration each visit, twice per week for three weeks and then once per week for 3-5 weeks. There will be a 4-8 week washout period between Visit 11 and Visit 12.
6. For the subgroup of subjects enrolled in the 1 time hourly treatment visit of Aim 3, they will receive the above mentioned MRI and nonMRI measures before and immediately following the 1x hourly treatment. The PSFS and UEFI questionnaires will not be administered for this 1x treatment visit only. The participants will undergo (i.) CDT alone, (ii.) CDT with graded negative pressure, or (iii.) exercise and self management treatment. This subgroup participation may involve undergoing all three of the single treatment options on different study dates if the participant is interested otherwise the study only only involves this one-time study visit.

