7. Post processing of this MRI data will be overseen by [name] and performed by [name] or a member of the KSP team. The KSPs analyzing the data in Aim 3 will be blinded of the subjects' group assignments until after data processing and statistically analysis.
8. Images from cases showing examples of findings that correlate with changes in lymphatic structure and function will be de-identified before inclusion in any potential publication or presentation of the results of this pilot study and saved by [name].

9. Compensation will be as follows:
 - a. Aim 1 = \$60
 - b. Aim 2 = \$20 (non-MR measures) / \$40 (MRI)
 - c. Aim 3
 - i. Scan 1 for 1st Treatment = Choice of check for \$60 OR 1 Velcro day and night-time compression wrap for arm and hand
 - ii. If all 9 treatments + exit visit MRI/non-MRI measures complete = \$60
 - iii. After 4-8 month washout period
 - iv. Scan 1 for 2nd Treatment = \$60
 - v. If all 9 treatments + secondary MRI complete = \$60
 - vi. If completes all parts of the study, will earn additional \$50
 - vii. Total = \$120+\$120+\$50 = \$290 OR Total = 1 Velcro compression garment (free) + \$60 + 120 + \$50 = \$230 + 1 Velcro compression garment
 - d. Subgroup Aim 3 each one-time visit treatment (pre and post MRI and non MRI measures = \$80

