10.0 Follow-up

No specific follow-up scans are required for Aim 1 unless patients are eligible and would like to enroll in the 2-year monitoring aim of the study (Aim2). For Aim 2, subjects will be able to contact the PI and co-investigators with any questions and a KSP will contact them to schedule their 6-8 month follow up visits for a total of 4 within the 2 year monitoring period. For Aim 3, subjects will be scheduled for all treatment visits prior to start of each course of treatment (Visits 2-10 and 13-21). The subjects will be able to contact the KSP with any questions and needs to change their assigned treatment times and dates should any adjustments be necessary. The subjects will be contacted during their washout period to schedule their second course of treatment visits and intake and exit measurement visits. An unwillingness to participate in any future scans or treatments will not influence or disqualify a volunteer from participating in the first instance. For the one-time treatment subgroup of Aim 3, this is a one-time visit for the pre and post MRI and nonMRI measures with no further study follow-up unless the participant wishes to undergo all three separate treatment interventions at different dates for interperson treatment comparison. For participants in Aim 2 (monitoring period), if the lymphedema specialist recommends lymphedema management, then the subject will be encouraged to seek out clinical care which does not prevent them from being able to participate in this study, including patients being monitored over 2-years. The lymphedema specialist will help the client obtain orders and location of treatment if subject would like assistance.

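### Aim 3 requires a washout before the second course baseline but no interval since earlier therapy before the first, so comparability of the two baselines is not assured

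*Combined protocol and SAP*

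**What the plan says.** **Entry.** The only Aim 3 inclusion criterion (Section 3.0) is an adult woman "diagnosed with unilateral secondary lymphedema in the upper quadrant and/or extremity following cancer related surgery involving removal of any axillary lymph nodes and/or radiation therapy". The exclusion closest to treatment history is "Persons who are deemed clinically unsuitable for an MRI or lymphedema therapy by their treating physician", which concerns suitability, not timing. Section 5.0, item 1 describes the entry screen as covering "MRI contraindications or MLD contraindications or precautions to determine eligibility of the study".

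**Intervals.** Section 5.0, item 5 schedules "non-MRI and MRI measures (#2) at Visits 1, 11, 12 and 22". Visits 1 and 12 are the two course baselines. The same item states: "There will be a 4-8 week washout period between Visit 11 and Visit 12". The compensation list in Section 5.0, item 9 instead reads "After 4-8 month washout period". No interval is stated before Visit 1.

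**Therapy outside the study.** Section 2.0 calls both treatments common practice and adds that "the Vanderbilt Lymphedema Clinic utilizes the graded negative pressure therapy as a component of treatment". Section 4.0, item 1 assures patients that their clinical care stays the same whether or not they take part.

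**One-time subgroup.** Section 10.0 describes a single visit without further follow-up "unless the participant wishes to undergo all three separate treatment interventions at different dates for interperson treatment comparison". Neither that section nor Section 5.0, item 6 says whether a cross-over participant may also attend.

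**Order and analysis.** Section 5.0, item 5 gives Group 1 and Group 2 the same order: CDT alone, then CDT with negative pressure. Section 8.0 compares pre-to-post change between the two therapies, first with a paired t-test or signed-rank test. A general linear model with treatment and treatment-period interaction follows. No course baseline is named as a covariate.

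**The concern.** Requiring a washout before Visit 12 accepts that the effect of a treatment course can last into a later baseline. The same reasoning applies to the same therapies received before Visit 1. Entrants already have the diagnosis, the therapies are in routine use, and some entrants are reached through their clinicians, so recent treatment at entry is plausible. A woman could have Visit 1 shortly after clinic CDT, with or without negative pressure, or after a one-time study session.

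The primary contrast is a difference between two changes, each measured from its own baseline. If the baselines differ in how much earlier treatment they carry, the changes differ for a reason unrelated to the treatment under study. The planned carry-over test looks at course 1 into course 2. It is not aimed at therapy brought into course 1 from outside.

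**Working it through.** **The plan's own figure.** Section 8.0 states 80% power for a 40% reduction rate at one-sided 5%. It cannot be reproduced, because the sample size, standard deviation, underlying rates and the endpoint behind that rate are not given. The point below does not depend on it.

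**Step 1: the two baselines side by side.**

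| | Visit 1 | Visit 12 |
|---|---|---|
| Required interval since therapy | none stated | 4-8 weeks (item 5) or 4-8 months (item 9), after the study course |
| Outside therapy restricted | no | no; the washout is not defined that way |
| One-time study visits kept out | no | no |
| Who has had prior therapy | unknown share | every woman who completed course 1 |

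**Step 2: net difference between courses.** All inputs here are assumed; the documents give none. Let D be the mean change over a course that starts with no residual effect, s the share of entrants recently treated, r1 the fraction of D still present in them at Visit 1, and r2 the mean fraction of D present at Visit 12. Take the two treatments as equally effective and effects as additive.

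- Course 1 change = D(1 − s × r1)
- Course 2 change = D(1 − r2)
- Course 2 minus course 1 = D(s × r1 − r2)

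| s | r1 | Difference if r2 = 0 | r2 at which it is zero |
|---|---|---|---|
| 0.25 | 0.20 | 0.05D | 0.05 |
| 0.50 | 0.30 | 0.15D | 0.15 |
| 0.75 | 0.50 | 0.375D | 0.375 |

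The third column is an upper bound for each row. Above the r2 in the last column the sign reverses: with s = 0.5, r1 = 0.3 and r2 = 0.30, the difference is 0.15D − 0.30D = −0.15D.

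**Step 3: effect on the test.** Let b be the course difference in standard deviations of the within-woman difference, with no true treatment effect. For a single order, the error of a one-sided 5% paired t-test is the upper tail of a noncentral t with n − 1 degrees of freedom and noncentrality b√n. For a 1:1 balanced order, 20,000 simulated trials were run per setting. Both n and b are assumptions.

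| n | b | Same order in both groups | Balanced, period-adjusted | Balanced, unadjusted |
|---|---|---|---|---|
| 10 | 0.2 | 14.5% | 4.8% | 4.4% |
| 10 | 0.4 | 31.7% | 5.2% | 4.2% |
| 10 | 0.6 | 54.3% | 5.1% | 2.9% |
| 20 | 0.2 | 21.7% | 5.0% | 4.8% |
| 20 | 0.4 | 53.2% | 5.0% | 3.8% |
| 20 | 0.6 | 82.7% | 5.4% | 3.0% |

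To link the steps: a difference of 0.15D gives b = 0.2 only if D is 0.2/0.15 = 1.33 of these standard deviations. The table takes b as favouring the second course. With the opposite sign, the one-sided error would fall below 5% and power would be lost.

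**Step 4: can the planned model correct it?** With two opposite orders and a period term, a common shift between courses cancels from the treatment estimate. With one order, treatment and period are the same contrast, and no model can separate them.

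**The case against.** The other side has several fair points, and they limit what can be claimed.

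- **One clean and one contaminated baseline.** A reader might infer this from the washout, and conclude that the baselines are not comparable. The documents do not support it. The washout is not defined as treatment-free and clinical care is unchanged, so both baselines are uncontrolled. What follows is that comparability is not assured.
- **An error favouring negative pressure.** This is tempting because negative pressure comes second as printed. It holds only if s × r1 exceeds r2. Every completer has just had nine study treatment visits before the washout, so r2 may be the larger term.
- **Recruitment from the clinic that gives negative pressure.** No section names that clinic as the Aim 3 source. Section 4.0 lists clinicians, flyers, databases and support groups. The missing limit applies to all of them, and the share recently treated is unknown.
- **Bias depends on the sequences.** This stands. If the identical orders are a misprint and the orders are balanced, Step 3 shows no inflation; what remains is added variance and a period effect.
- **The one-time subgroup reads as a separate track.** It does, but no passage prevents overlap. Whether a one-hour session leaves a lasting effect is not known.
- **The MLD screening form may already ask about recent therapy.** Its content is not in the documents. It is described only as a screen for contraindications or precautions.

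None of this supplies the missing interval before Visit 1 or a rule for outside therapy during the washout.

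**Conclusion.** The point holds in a limited form. Aim 3 sets an interval before Visit 12 and none before Visit 1, leaves outside therapy unrestricted before both, and does not keep one-time visits out of either period. The course baselines are taken under different and uncontrolled prior-treatment conditions, so their comparability is not assured.

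The consequence depends on the order. Balanced orders with a period term keep the error rate near 5% at some cost in precision. Under the single order printed, any baseline difference is fully confounded with treatment. The 0.05D to 0.375D figures are upper bounds under assumed inputs, and neither size nor net direction can be determined from the documents. The omission should be corrected because it touches the primary contrast and the remedy is small.

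**What to change.** 1. Reconcile the washout length between items 5 and 9 of Section 5.0, and reconcile the Group 1 and Group 2 sequences in item 5.
2. Schedule Visit 1 so that the time since the last CDT or negative-pressure session, from any source, is at least the protocol's own reconciled interval before Visit 12. This is a rule about when to enrol; no care is withheld for the study. Ask for the date when Visit 1 is booked.
3. Record the date and type of the last outside session at Visit 1, on the MLD screening form already completed then, and again at Visit 12. State how outside therapy during the washout is handled in the analysis.
4. Do not schedule one-time subgroup visits for a cross-over participant from the start of the interval in point 2 until Visit 22.
5. Name period and course baseline as terms in the Section 8.0 linear model. This does not rescue a single-order design, so point 1 comes first.

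The cost is one entry criterion, one or two data fields, one scheduling rule and a sentence in Section 8.0. The downside is that some women enter later, by an amount that depends on the reconciled washout, and women in continuous clinic care may be deferred.
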